- This visit will first take place with a research coordinator where the participant will be allowed to ask any final questions about their consent which will then be signed either on paper or electronically.
- Final eligibility will be determined by a licensed medical provider on the research team by ensuring the participant is not experiencing any symptoms of pyelonephritis and/or sepsis.
- Consented study participants will then complete baseline questionnaires including the Urinary Tract Infection Symptom Assessment (UTISA)⁶⁸ and the pelvic floor distress inventory short form (PFDI-20).⁶⁹
- Participants will submit a urine specimen for urine culture and urinalysis either in-person at one of our Women's Center for Bladder and Pelvic Health faculty practices or a local laboratory

Randomization: Participants will be randomized by the study team to either the “Culture-directed Antibiotic Treatment” or “Empiric (Immediate) Antibiotic Treatment” Group in a 1:1 allocation scheme, with randomization using permuted blocks of 4 or 6.

D.1.3.3 Antibiotic Treatment Strategy. All participants will be allowed to use acetaminophen, non-steriodals, and/or phenazopyridine.

Culture-directed Antibiotic Treatment: Participants will be directed to refrain from taking antibiotics until results of urine culture are reported, which is expected within 48-72h.

Empiric Antibiotic Treatment Participants will be prescribed empiric antibiotics in accordance with our stepwise protocol below.

Antibiotic Protocol. For participants in the empiric Rx arm, we will choose an antibiotic with consideration of patient reported allergies, current medications and current IDSA guidelines.⁷⁰ If there is a contraindication to the first antibiotic on the list they will progress to the next option until a suitable selection is achieved.

Antibiotic Protocol:

1. Nitrofurantoin 100 mg PO BID x 5 days
2. Trimethoprim/Sulfamethoxazole 875/125 mg PO BID x 5 days
3. Fosfomycin 3 g once
4. Cephalexin 500 QID x 5 days
5. Ciprofloxacin 500 mg PO BID x 5 days

D.1.3.4 Antibiotic management after urine culture results. All participants will be called with the results of their culture. Participants who register for *MyUPMC*, a no-cost, proprietary secure email service, will also receive the urine culture result by email. Cultures with result of “mixed flora” will be considered contaminated and be managed as negative.⁷¹

Culture-directed Antibiotic Treatment.

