- Those with a negative urine culture will not be prescribed antibiotics and will be followed per protocol.
- Those with a positive urine culture who *report persistent UTI symptoms* will be given antibiotics following the priority list above with consideration to reported antimicrobial sensitivities.
- Those with a positive urine culture who *report resolution of UTI symptoms* will not be given antibiotic

Empiric Antibiotic Treatment.

- Those with a negative urine culture will be told to stop antibiotics
- Those with a positive urine culture sensitive to the empiric antibiotic will be instructed to complete the full course of their antibiotics
- Those with a positive culture resistant to empiric antibiotic will be given an alternative antibiotic per antibiotic protocol and will be followed per protocol. If there are no oral antibiotic options with patient-specific and antimicrobial sensitivities, we will engage local infectious disease physicians for management as per standard clinical protocols.

[figure not shown]
D.1.6. Study follow-up assessments.

All participants will be followed with electronic surveys via Research Electronic Data Capture (REDCap) software, which is a browser-based, metadata-directed EDC software and workflow methodology for designing

clinical and translational research databases,⁷² on day 2-3 (after result of urine culture). To avoid limiting enrollment to only those with access to technology, our research coordinator can also call and administer the questionnaire by phone to ensure ability to access and complete electronic materials. Follow-up assessments will be completed weekly for a total of 4 weeks. These will include UTISA questionnaire,⁶⁸ antibiotic associated side effects, use of other symptom mitigating remedies, and adherence to assigned study arm.

Participants will be provided with a clinical line to call 24/7 with report of worsening symptoms which will be discussed with the PI, [name] for determination of antibiotic prescription and if participants report fevers or chills this will prompt an in-person evaluation in clinic during business hours or the emergency department after hours. If participants call to report new symptoms during the study course, a repeat urine culture will be obtained.⁷³ Given that these episodes could be considered either a recurrent or incompletely treated infection we plan to manage these per clinical care and not based on the participants initial study arm.

Figure 2: Study Flow Diagram

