
Pelvic floor distress inventory, PFDI-20; Urinary Tract Infection Symptom Assessment, UTISA
 * Adverse events will include either antibiotic related side effects, signs/symptoms of pyelonephritis and/or urosepsis or other serious adverse events

D.1.7. Data analysis.

Specific aim 1A) To evaluate the feasibility of recruiting eligible participants into a randomized trial of a culture-directed versus empiric antibiotic strategy for patient-reported UTI symptoms in older women.
 All outcomes for the feasibility assessment will be descriptive using numbers and proportions of patients and 95% CIs. We will report the number of patients assessed for eligibility along with the numbers excluded based on not meeting inclusion criteria, participation declined, and other reasons.⁷⁴ We will document number and proportion of enrolled participants who were randomized along with the number/proportion who received their

allocated assignment. We will document those lost-to follow-up including potential reasons. These data will provide information on the feasibility of recruiting patients into a future, large randomized, placebo controlled clinical trial. We believe that successfully recruiting 10% of eligible patients (e.g., 6-7 patients per month) will confirm the capacity to recruit for a future trial.

Power calculation:^{75,76} The primary outcome is feasibility which we will define as the ability to recruit 10% of eligible patients. As this is a pilot study, the sample size of 70 patients was determined based on clinical and logistical resources rather than statistical requirements for hypothesis testing. We anticipate screening approximately 1200 potentially eligible patients (based on known clinical data from our practice and current enrollment of women with recurrent UTI in Pitt+Me®) during the 12 months of recruitment (~100 per month) of which at least 800 will be deemed eligible and have UTI symptoms. (~67 per month) This is based on data from our group on urine cultures sent annually and time between UTI episodes.³⁵ A 95% confidence interval (CI) for the recruitment rate provides a 2.4% margin of error (MoE) assuming the true rate is 10%.

Specific aim 1B) To evaluate participant adherence to study procedures.

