For a larger trial, electronic surveys may significantly reduce research coordinator burden. To evaluate feasibility of this approach we will administer electronic surveys through Research Electronic Data Capture (REDCap) software.⁷² Surveys are sent via email and can be accessed through either a laptop, desktop or smart phone. Participants will also be called at day 2-3 (after urine culture results) and then weekly to assess issues with electronic materials. We will evaluate proportion of those with electronic success and investigate demographic variables that may be associated with inability to utilize electronic materials. To assess patient adherence to study procedures, defined as completion of all follow-up questionnaires, we will describe the percentage of enrollees who completed 100% of study procedures, 80% to 100% of study procedures and 50% to 80% of study procedure. A priori, we believe that compliance with 70% of study procedures will demonstrate satisfactory patient adherence to protocol. If the underlying adherence rate is 70%, a sample size of 70 provides a 10.1% MoE.

Exploratory Aim: To explore the safety of a culture-directed UTI treatment strategy and preliminary secondary outcomes of assigned treatments.

Safety Aims⁶²

1. Adverse events per group (most likely antibiotic side effects (i.e., gastrointestinal distress, antibiotic related diarrhea, rash) between groups.
2. Serious adverse events per group (defined in line with FDA reporting guidelines as a medical event that does one or more of the following: results in death, is life - threatening, requires inpatient hospitalization or prolongation of existing hospitalization, results in persistent or significant disability/incapacity, or is a congenital anomaly/birth defect.⁷⁷

Analysis. We anticipate that adverse events will be reported relatively infrequent.⁷⁸ All outcomes will be described using numbers and proportions of patients. Proportions between groups will be compared with either chi-square or Fischer's exact testing.

Secondary exploratory aims.

Proportion of those with clinical cure (as 2 or less points (slight, very slight, or no problems) on all five components of the UTISA (ref) at day 14 (***future trial primary outcome***)

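### The adverse-event definition and survey item tie common non-serious events to antibiotic causation, with no all-cause capture described, which could tilt the exploratory safety comparison towards the culture-directed arm

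*Combined protocol and SAP*

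**What the plan says.** Three places bear on which non-serious events are recorded.

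- **Figure 2 footnote:** "Adverse events will include either antibiotic related side effects, signs/symptoms of pyelonephritis and/or urosepsis or other serious adverse events". The only residual category is limited to serious events.
- **D.1.6 (follow-up):** "All participants will be followed with electronic surveys via Research Electronic Data Capture (REDCap) software", first at day 2-3, and then "Follow-up assessments will be completed weekly for a total of 4 weeks". Besides the UTISA, the listed content is "antibiotic associated side effects, use of other symptom mitigating remedies, and adherence to assigned study arm". No general adverse-event question is listed.
- **D.1.7, Safety Aim 1:** "Adverse events per group (most likely antibiotic side effects (i.e., gastrointestinal distress, antibiotic related diarrhea, rash) between groups". This is wider, since antibiotic side effects are named as the likely majority and not as the only events. Proportions are compared between arms by chi-square or Fisher's exact test. Serious events are defined separately and for any cause.

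Antibiotic exposure differs between arms by protocol. Under D.1.3.3 every woman in the empiric arm is prescribed an antibiotic at the start. In the culture-directed arm, D.1.3.4 says: "Those with a negative urine culture will not be prescribed antibiotics and will be followed per protocol". Women in that arm with a positive culture whose symptoms have resolved also get none. Both arms may use symptom relief: "All participants will be allowed to use acetaminophen, non-steriodals, and/or phenazopyridine".

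**The concern.** Diarrhoea, nausea or rash in a woman taking an antibiotic fits the footnote and the survey item. The same symptom in a woman who took none fits neither, unless it is serious or a sign of ascending infection. Side effects of the permitted symptom-relief drugs are also not named, although use of other remedies is recorded. Because the plan withholds antibiotics from part of one arm only, the chance that a background symptom is recorded depends on the randomised arm. This is differential ascertainment.

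What is at stake is an exploratory comparison, but one with a purpose. Section C says the pilot is to develop the data collection forms and to establish preliminary safety data that will matter for patient and provider engagement in the future trial. A form that under-records one arm would bias that evidence and could be carried into the definitive trial. Symptoms that were never asked about cannot be recovered afterwards.

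**Working it through.** The documents give no adverse-event rate, difference or power, so there is no stated figure to reproduce. The check asks how large the distortion would be if the footnote were applied strictly.

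**Inputs from the documents**

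- Culture-negative share under expectant management (section B.2, Table 1): 50/122 = 41.0%. The positive share is 72/122 = 59.0%.
- Symptom improvement in that cohort: 20/78 = 25.6%. This is a rough upper proxy for resolution, because improvement is not resolution.
- Arm size: 70 women randomised 1:1, so 35 per arm.

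**Share of the culture-directed arm without a protocol antibiotic (u)**

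- Negative cultures only: u = 0.410, and 0.410 × 35 = 14.3, about 14 women.
- Adding culture-positive women who improve: u = 0.410 + 0.590 × 0.256 = 0.561, and 0.561 × 35 = 19.6, about 20 women.
- Empiric arm: 0 by protocol.

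**Recorded rates**

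Let b be the background rate of common events over four weeks (assumed). It is the same in both arms, antibiotics have no true effect, and every event in an antibiotic user is attributed to the drug. Recorded rates are then b in the empiric arm and b(1 − u) in the culture-directed arm. The ratio is 1 − u, which is 0.59 at u = 0.410 and 0.44 at u = 0.561. The gap is b × u. The last column assumes instead that only about one week in four falls close enough to a course for attribution, so it is b × u / 4.

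| b (assumed) | Empiric | Culture-directed | Gap, points | Gap if one week in four is attributed |
|---|---|---|---|---|
| 5% | 5% | 3.0% to 2.2% | 2.0 to 2.8 | 0.5 to 0.7 |
| 10% | 10% | 5.9% to 4.4% | 4.1 to 5.6 | 1.0 to 1.4 |
| 20% | 20% | 11.8% to 8.8% | 8.2 to 11.2 | 2.0 to 2.8 |
| 30% | 30% | 17.7% to 13.2% | 12.3 to 16.8 | 3.1 to 4.2 |

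A shorter attribution window shrinks the absolute gap but leaves the ratio unchanged. The 41.0% is itself imprecise: its 95% Wilson interval is 32.7% to 49.9%, giving ratios of 0.67 to 0.50.

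**Separating artefact from real benefit**

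Let a be the true excess risk from an antibiotic. All-cause counting gives a difference of a × u. Strict attribution gives (a + b) × u. With a = b = 10% (both assumed), all-cause counting shows 4.1 to 5.6 points and strict attribution 8.2 to 11.2 points, so half of the latter is artefact.

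**Chance of a false significant result**

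For Fisher's exact test, two-sided 0.05 (assumed), 35 per arm, every event in an antibiotic user attributed and no true effect, the probability is 0.3% at b = 5%, 2.3% to 3.6% at 10%, 8.9% to 16.4% at 20%, and 15.2% to 30.3% at 30%. When both arms are counted alike it is 0.3% to 2.8% over the same range. At low background rates the problem is a biased estimate more than a false test result.

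**The case against.** The strongest reply is that the plan is ambiguous, not closed. The footnote says what adverse events will include, Safety Aim 1 only predicts which events will dominate, and all women receive the same follow-up. The survey itself is not in the documents, so its side-effect heading might stand for a symptom checklist put to everyone. This stands, and it rules out a reading that a reader might infer: that untreated women cannot contribute a common event and that the comparison is settled by construction. It does not dispose of the point. A wide aim cannot restore events that a narrower question did not collect, and no section says how a symptom in an untreated woman is recorded.

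Other parts of the reply also stand:

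- About 14 of 35 is not a floor. Under D.1.6, worsening symptoms can lead to an antibiotic decision and new episodes are managed by clinical care, not by arm. The statistical methods table counts off-protocol antibiotics in the culture-directed arm. The proxy cohort was also non-randomised, and only 52.0% had recurrent UTI.
- Attributing four weeks of background events to an antibiotic is generous, because the listed courses are a single dose or 5 days and culture-negative women in the empiric arm are told to stop. Rates of 20% to 30% also sit poorly with the expectation in D.1.7 that events will be infrequent.
- Fewer side effects from fewer antibiotics is a genuine effect of the strategy.
- A reader might infer that waiting women will lean more on non-steroidals and phenazopyridine, or that women will judge relatedness themselves. The documents say only that both arms may use these drugs, and do not say who judges relatedness. The point needs neither inference.

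**Conclusion.** The concern holds as a matter of unreconciled and too narrow wording. The footnote and the survey item tie non-serious events to antibiotic causation or ascending infection, Safety Aim 1 is broader, and all-cause capture of non-serious events is nowhere described. If the narrow wording is applied, the comparison of common non-serious events tilts towards the culture-directed arm, in addition to any real benefit.

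The size cannot be fixed from the documents. A recorded rate ratio of about 0.59 follows if the cohort's 41.0% is the untreated share, there is no true effect and every event in an antibiotic user is attributed. It would be nearer 1 if untreated women later take antibiotics, and lower if many culture-positive women resolve. The absolute gap depends on the assumed background rate and attribution window. A reader might infer that the whole safety assessment is slanted. It is not: signs of pyelonephritis or urosepsis and any-cause serious events count in both arms, and the former could weigh against the culture-directed arm.

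The comparison is exploratory in a 70-woman feasibility pilot, so the weight is minor to moderate. It should still be corrected, because these forms and safety data are meant to inform the next trial.

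**What to change.** - Reconcile the Figure 2 footnote, the follow-up content in D.1.6 and Safety Aim 1 in D.1.7, so that all three use one definition.
- At every survey, ask all women in both arms the same symptom checklist (nausea, vomiting, abdominal upset, diarrhoea, rash, other), whether or not they took an antibiotic and without asking for a cause.
- Define the non-serious adverse-event outcome as any such event, by randomised arm, regardless of attribution.
- Report judged relatedness (antibiotic, other remedy) as a secondary breakdown, and state who makes the judgement.

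With equal background rates this removes the b × u artefact and keeps the genuine a × u difference. The cost is survey wording and one definition, with the same respondents and time points. The downsides are a slightly longer survey and a higher event count from background symptoms.

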D.1.1 Overview and Design. The proposed pilot study is designed as a culture-directed versus empiric antibiotic strategy for patient-reported UTI symptoms in older women. (Figure 2) Over 12 months, we will recruit 70 women with rUTI. Following enrollment, patients will be randomized in a 1:1 ratio to one of two groups. Patients assigned to the culture-directed arm will await results of urine culture prior to potentially receiving antibiotics and those assigned to the empiric arm will be prescribed immediate antibiotics from an established list of commonly prescribed antibiotics. Participants will be sent electronic questionnaires after urine culture results and then weekly for a total of 4 weeks. The primary outcome is feasibility of trial defined as recruitment of 10% of eligible participants with 70% adherence to study protocol.

D.1.2 Recruitment and Subject Eligibility. Women age ≥65 years⁶¹ with diagnosis of recurrent UTI (rUTI) will be recruited from: 1) UPMC WCBPH faculty practices or 2) CTSI Pitt+Me® Research Registry. Eligibility criteria are listed in Table 2.

Rationale for Inclusion Criteria: We will include participants with patient reported recurrent UTI to allow for a pragmatic study design and generalizability. Additionally, our definition of patient reported UTI is like other RCTs evaluating non-antibiotic options as compared to antibiotic strategies for UTI treatment.^{43,62} We will exclude participants with features of complicated UTI in the setting of structural or functional abnormalities or instrumentation /catheterization^{4,63} Eligibility is limited to female biologic sex given the differential risk profile of males and females who experience recurrent UTIs.

D.1.3 Study procedures (Figure 2).

D.1.3.1 – Screening and Enrollment Procedures.

Information on the REDUCTION trial will be broadly disseminated in the University of Pittsburgh faculty practices at the WCBPH, through IRB approved brochures, social media ads, institutional (MWRI) and CTSI websites. Interested women will be encouraged to contact the research staff for more information. Women who meet eligibility criteria after screening will be provided a consent form via their preferred method (electronic or paper).

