Analysis. All outcomes will be described using numbers and proportions of patients or means with confidence intervals. Proportions between groups will be compared with either chi-square or Fischer's exact testing and means will be compared with student's t-testing. Exploratory logistic regression modeling will be utilized to investigate the odds of both initial treatment failure and/or recurrent of UTI symptoms between groups and based on baseline characteristics

Power analysis:^{76,79} As above, we propose a future trial with a primary outcome to be symptom resolution at day 14 defined as 2 or less points (slight, very slight, or no problems) on all five components of the UTI symptom assessment (UTISA).^{43,78} The literature suggests 58-80% of women receiving empiric antibiotics for patient reported UTI will achieve clinical cure by day 3-7 after treatment initiation.^{43,78} Given that only women

with a positive urine culture will be given culture-directed antibiotics, and women in the empiric arm may have to have their antibiotics changed or stopped at the time of culture result, we anticipate a higher proportion of those in the culture-directed arm to have symptom resolution at day 7. Assuming 70% symptom resolution in the empiric arm, a future trial of 262 participants, with 131 per arm, would have 80% power to detect a 15-percentage point difference between groups with a 2-sided alpha of 0.05, while a sample size of 300 would be required assuming 65% resolution. Therefore, we believe that successfully recruiting a total of 70 participants at a rate of 6-7 participants/month will confirm the feasibility of future trial completion in <4 years (equivalent to other trials of antibiotic regimens for symptomatic UTI).^{17,78}

Statistical methods

Primary Outcomes	Statistical analysis
Feasibility: 
 - Number of subjects that were screened for participation - Number and proportion of subjects screened who met inclusion/exclusion criteria - Number and proportion of subjects who either declined participation or were ineligible (including reasons for ineligibility) - Number and proportion of eligible subjects that were enrolled in the study - Number and proportion of subjects enrolled who completed the study - Monthly enrollment rate 	Descriptive analysis = counts and proportions or means with standard deviation

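### The 10% recruitment criterion, the 70 places and the 800 eligible women do not agree over the stated 12 months (70/800 = 8.75%), no closing point for the denominator is given, and the 2.4% margin of error does not follow from 800

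*Combined protocol and SAP*

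**What the plan says.** Section D.1.1 (Overview and Design) sets the criterion: "The primary outcome is feasibility of trial defined as recruitment of 10% of eligible participants with 70% adherence to study protocol". The same section sets size and duration: "Over 12 months, we will recruit 70 women with rUTI".

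Section D.1.7, Specific aim 1A, restates the criterion with a monthly equivalent: "We believe that successfully recruiting 10% of eligible patients (e.g., 6-7 patients per month) will confirm the capacity to recruit for a future trial". Its Power calculation repeats it ("The primary outcome is feasibility which we will define as the ability to recruit 10% of eligible patients") and explains that 70 was chosen on resources, not by a hypothesis test. It expects about 1200 women screened "during the 12 months of recruitment (~100 per month) of which at least 800 will be deemed eligible and have UTI symptoms", or about 67 per month. On precision it says "A 95% confidence interval (CI) for the recruitment rate provides a 2.4% margin of error (MoE) assuming the true rate is 10" (per cent), without naming the n.

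The later Power analysis for the future trial joins the total to the monthly rate: "successfully recruiting a total of 70 participants at a rate of 6-7 participants/month will confirm the feasibility of future trial completion in <4 years". The Statistical methods table lists "Number and proportion of eligible subjects that were enrolled in the study" and the monthly enrolment rate as feasibility outcomes. Neither entry says when counting begins or ends.

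**The concern.** The 70 recruits and the 800 or more eligible women are both attached to the same 12 months, and their ratio is below the 10% that defines success. Because 800 is given as a minimum, a larger number of eligible women would lower the ratio further. A pilot that filled every place on schedule could therefore miss its own recruitment criterion.

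The missing rule is the point at which eligible women stop being counted. If that is settled only once the data are in, the same patients and the same uptake can be reported as meeting 10% or as missing it. The plan treats reaching 10% as confirmation that a future trial can recruit, so the choice affects the conclusion drawn.

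The margin of error is a separate and smaller matter. The stated value does not correspond to the only eligible count the plan gives.

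**Working it through.** **Inputs.** Criterion 10% (D.1.1, D.1.7); 70 women over 12 months (D.1.1); at least 800 eligible over 12 months, about 67 per month (D.1.7); 6-7 enrolled per month (D.1.7, Power analysis); stated margin of error 2.4% for a 95% CI at a true rate of 10%, n not given (D.1.7).

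**1. The plan's margin of error.** Wald half-width = 1.96 × √(p(1 − p)/n). With p = 0.10 and n = 800: 1.96 × √(0.09/800) = 2.08%. The stated 2.4% is not reproduced. Half-widths by method:

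| n | Wald | Wilson | Clopper-Pearson |
|---|---|---|---|
| 600 | 2.40% | 2.41% | 2.48% |
| 700 | 2.22% | 2.23% | 2.29% |
| 800 | 2.08% | 2.08% | 2.14% |
| 1200 | 1.70% | 1.70% | 1.74% |

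Other variants at n = 800 also fail to give 2.4%: Agresti-Coull 2.09%, Jeffreys 2.08%, continuity-corrected Wald 2.14%, a 90% interval 1.74%, a 99% interval 2.73%. The widest single arm of a 95% interval at n = 800 is 2.29% (Clopper-Pearson, upper). Solving the Wald formula for n gives 0.09 × (1.96/0.024)² ≈ 600, or 576 to 626 allowing for rounding of 2.4%. No count near 600 appears in the documents.

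**2. The criterion with the full 12-month denominator.**
- Rate at full enrolment: 70/800 = 8.75% (Wilson 95% CI 7.0% to 10.9%).
- Women needed for 10%: 0.10 × 800 = 80.
- Monthly enrolment for 70 in 12 months: 70/12 = 5.8, below the stated 6-7.
- At 6-7 per month for 12 months: 72 to 84 women, not 70.

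**3. The criterion if counting stops at the 70th enrolment.**
- Eligible per month: 800/12 = 66.7; 10% of that is 6.7 per month, within the stated 6-7.
- Eligible women needed: 70/0.10 = 700.
- Time: 700/66.7 = 10.5 months.

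The percentage, the monthly rate and the total of 70 then agree.

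**4. How far the counting rule decides the result.** Take a true uptake of exactly 10% and judge the point estimate, with X binomial:

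| Counting rule | Condition for a rate of at least 10% | Probability |
|---|---|---|
| Stop at the 70th enrolment | 70th reached within 700 eligible, P(X ≥ 70, n = 700) | 0.518 |
| Count 800, enrolment not capped | P(X ≥ 80, n = 800) | 0.517 |
| Count 800, enrolment capped at 70 | maximum is 70/800 = 8.75% | 0 |

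In the capped case all 70 places would be filled within 800 eligible women with probability P(X ≥ 70, n = 800) = 0.894. The criterion would still be missed every time.

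**The case against.** The strongest reply is that the failure needs three things together, none stated in the plan: enrolment capped at 70, eligible women still counted after enrolment closes, and judgement on the point estimate. A woman who presents after enrolment has closed cannot be recruited, so counting her as a recruitment failure is an unnatural reading. If counting ends with enrolment, 70 women at 6-7 per month take 10.0 to 11.7 months, which fits within 12 months and agrees with 10%. With no cap, the full-year denominator does no harm either (0.517 against 0.518). The zero follows from the cap by construction.

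Much of this stands, and it is why the conclusion is conditional. It does not remove the gap. The plan ties both 70 and 800 to the same 12 months, sets 70 on resources so that a cap is plausible, and nowhere says that counting ends with enrolment.

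On the margin of error, no n is given, so the mismatch could be an unstated input rather than a slip. The back-solved 600 is also not unique: the upper arm of an asymmetric interval is 2.39% at n = 700 (Jeffreys) and 2.41% at n = 720 (Wilson). But no arm at n = 800 exceeds 2.29%. The gap of about 0.3 percentage points is conservative and changes no decision.

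It is also fair that the outcomes are descriptive, that no automatic go/no-go rule hangs on 10%, that the CI for 70/800 includes 10%, and that a reader could recompute the rate from the reported counts.

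**Conclusion.** The concern holds as stated. Taken over the 12 months that the plan names, 70 places and at least 800 eligible women give at most 8.75%, 10 women short of the 80 that 10% requires. This conclusion rests on enrolment stopping at 70, eligible women being counted to month 12, and the point estimate being judged. If counting closes at the 70th enrolment, about 700 eligible women give exactly 10%. The plan does not choose between these readings, and does not say whether the point estimate or the CI is judged.

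The 2.4% margin of error cannot be obtained from 800 eligible at a 10% rate: the half-width is 2.08% to 2.14%. This part is secondary.

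The point should be fixed because it concerns a component of the primary outcome. Its practical effect is limited by the descriptive analysis and by the reporting of the underlying counts.

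**What to change.** Keep the 10% criterion and the 70% adherence requirement. In D.1.1, D.1.7 and the Power analysis, add one defining sentence, for example: *The recruitment rate is the number enrolled divided by the number of eligible symptomatic women, counted until the 70th enrolment or 12 months, whichever comes first.* The expected figures are then about 700 eligible, 10.5 months, 6.7 per month and a margin of error of about 2.2%. That margin is approximate, because the denominator is random when counting stops at a fixed number enrolled.

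If the sponsor prefers to count eligible women for the full 12 months with enrolment capped at 70, restate the expected rate as 8.75% of 800 (5.8 per month, margin of error 1.96 × √(0.0875 × 0.9125/800) ≈ 2.0%). Then reconcile the 10% threshold with it before recruitment starts.

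Under either option, replace the 2.4% with a figure that names its n and method, and state whether the criterion is judged on the point estimate or on the confidence interval.

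The cost is a few sentences and one corrected number, with no extra patients or data. The first option leaves both parts of the criterion unchanged; the second requires the 10% threshold to be reconsidered.
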